6.1.4. Prior Therapy

The prior systemic cancer therapy regimens will be listed for all participants in the FAS. The component drugs of prior systemic therapy regimens will be coded using the WHO Drug Dictionary. The prior systemic cancer therapy regimen name, component drugs, start and stop dates, purpose of the regimen, best response, reason for discontinuation, and date of relapse/progression will be listed for all participants in the FAS.

The prior radiotherapy type, body site, start and stop dates, total dose, and best response will be listed for all participants in the FAS.

The date and description of the prior surgery/procedure for disease under study will be listed for all participants in the FAS.

6.1.5. Medical History

For participants in the FAS, medical history will be listed. This list will include the medical history event for each body system/organ class as documented on the eCRF.

6.2. Disposition of Participants

The treatment group, that is, if the treatment is ongoing or discontinued, and the primary reason for treatment discontinuation, or if the participant is still in study or withdrawal, and the primary reason for study withdrawal, will be listed for all participants in the FAS.

6.3. Exposure

For participants in the safety population, exposure to pemigatinib will be listed as the following:

- **Number of treatment cycles:**
Number of cycles with a nonzero dose of pemigatinib.
- **Duration of treatment with pemigatinib (days):**
Date of last dose of pemigatinib – date of first dose of pemigatinib + 1
- **Average daily dose of pemigatinib (mg/day):**
Total actual dose taken (mg) / duration of treatment with pemigatinib (days)
Total actual dose taken will be calculated based on the information entered on the Drug Accountability eCRF.
- **Pemigatinib dose modifications:**
Participants who had pemigatinib dose reduction and interruption.

6.4. Study Drug Compliance

For participants in the safety population, overall compliance (%) for pemigatinib will be calculated for all participants as

$$\text{Compliance (\%)} = 100 \times [\text{total dose actually taken}] / [\text{total prescribed dose}]$$

The total prescribed dose is defined as the sum of the doses prescribed by the investigator accounting for dose modifications.

The total actual dose taken will be calculated based on information entered on the Drug Accountability eCRF. If there are dispensed drugs that have not been returned yet, the actual dose taken starting from the dispense date of the unreturned drugs will be imputed by the dose taken as reported on the Dosing eCRF.

6.5. Prior and Concomitant Medication

Prior medications and concomitant medications will be coded using the WHO Drug Dictionary. The prior and concomitant medication will be listed for participants in the FAS by WHO drug class and WHO drug preferred term. In the data listing, each medication will be recorded as only prior, only concomitant, or both prior and concomitant.

7. EFFICACY

[Appendix A](#) provides a list of data displays.

7.1. Efficacy Hypothesis

Not applicable.

7.2. Analysis of the Primary Efficacy Parameter

7.2.1. Primary Efficacy Analysis

The primary endpoint of the study is ORR in Cohort A. Objective response rate is defined as the proportion of participants who achieve a CR or PR based on RECIST v1.1 ([Eisenhauer 2009](#)), as assessed by an ICR review committee. Confirmation of CR and PR is required and documented in the ICR charter. This analysis will be based on the FAS. Participants who do not have sufficient baseline or on-study response assessment information to be adequately assessed for response status will be included in the denominators in the calculation of ORR. The 95% CI for the ORR will be estimated using the Clopper-Pearson method.

7.2.1.1. Response Criteria

Overall disease status will be categorized and listed using RECIST v1.1 ([Eisenhauer 2009](#)). Participants will have their overall response evaluated as CR, PR, SD, PD, or NE at each postbaseline radiologic assessment based on changes in target lesions, nontarget lesions, and appearance of new lesions.

7.2.1.2. Objective Response Rates and Best Overall Response

A participant is considered an objective responder if they have a best overall response of CR or PR at any postbaseline visit prior to first PD.

In general, under the RECIST v1.1, BOR is the best response recorded postbaseline prior to and including the first PD, in the order of CR, PR, SD, PD, and NE. The BOR will be determined from response assessments before or on the same day as the new anticancer therapy. If any alternative cancer therapy is taken while on study, any subsequent assessment(s) will be excluded from the BOR determination. A BOR of CR or PR needs to be confirmed; the confirmation method is described in the ICR charter.

In the case of SD, measurements must meet the SD criteria at least once after the date of first dose (ie, a minimum interval of 42 days). Participants who fail to meet this criterion will have either a BOR of PD, if the next available assessment indicates PD, or NE, if there is no additional assessment available.

7.2.2. Subgroup Analyses for Primary Endpoint

Not applicable.

7.3. Analysis of the Secondary Efficacy Parameter

7.3.1. Secondary Endpoints Involving Objective Response Rate

The ORR in Cohort B is defined as the proportion of participants who achieve a CR or a PR based RECIST v1.1 as assessed by an ICR review. Confirmation of CR and PR is required and documented in the ICR charter. This analysis will be based on the FAS. Participants who do not have sufficient baseline or on-study response assessment information to be adequately assessed for response status will be included in the denominators in the calculation of ORR. The 95% CI for the ORR will be estimated using the Clopper-Pearson method.

7.3.2. Progression-Free Survival

Progression-free survival is defined as the time from the date of first dose of pemigatinib (Day 1) to the date of the first documented PD or death due to any cause, whichever is first. Progressive disease will be evaluated according to RECIST v1.1 and assessed by an ICR review. Partial death dates will be handled using the rules described in Section 4.1.4. Participants who are alive without progression, before the analysis cutoff date, will be censored. Censoring for PFS will follow the algorithm outlined in [Table 2](#) based on FDA guidance ([FDA 2015](#), [FDA 2018](#)).

Table 2: Evaluation and Censoring of Progression-Free Survival

Situation	Outcome	Date of Progression or Censoring
No baseline tumor assessments	Censored	Day 1
No valid postbaseline response assessments	Censored	Day 1
Progression documented between scheduled response assessments	Progressed	Date of first overall response of PD
No progression	Censored	Date of last valid radiologic assessment (not NE and not missing)
Study discontinuation for undocumented progression	Censored	Date of last valid radiologic assessment (not NE and not missing)
Study discontinuation for toxicity or other reason	Censored	Date of last valid radiologic assessment (not NE and not missing)
New anticancer treatment started	Censored	Date of last valid radiologic assessment (not NE and not missing) on/before starting a new anticancer treatment
Death before first PD assessment	Progressed	Date of death
Death between adequate response assessments	Progressed	Date of death
Death or progression after 2 or more missed assessments	Censored	Date of last valid radiologic assessment (not NE and not missing)

Progression-free survival data will be analyzed by the KM method in Cohort A. The number of participants who progressed or died and the number of participants censored will be summarized. The KM estimates of median PFS will be presented with its 95% CI. The 95% CI will be calculated using the generalization of Brookmeyer and Crowley's method (1982) with log-log transformation (Klein and Moeschberger 1997).

7.3.3. Duration of Response

For objective responders, DOR is defined as the time from the date that a participant first achieves CR or PR, until the date of first documented disease progression or death, whichever is first. Responses and PD will be evaluated based on RECIST v1.1 by an ICR review. The partial death dates will be handled using the rules described in Section 4.1.4. Participants who are alive without progression before the analysis cutoff date will be censored. Censoring of DOR will follow the same algorithm as the censoring of PFS (see Section 7.3.2).

The DOR data will be analyzed by the KM method in Cohort A. The total number of responders, the number of participants who progressed or died, and the participants censored will be summarized. The KM estimate of median DOR will be presented with its 95% CI. The 95% CI will be calculated using the generalization of Brookmeyer and Crowley's method (1982) with log-log transformation (Klein and Moeschberger 1997).

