3.2. Control of Type I Error

Unless otherwise specified, all CIs provided will be at the 95% confidence level.

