7.3.4. Overall Survival

Overall survival is defined as the time from the date of first dose of pemigatinib to the date of death due to any cause. Date of death will be determined using Death Report, Survival Follow-up, and Participant Status eCRFs. Participants who are lost to follow-up or still alive at the time of the analysis will be right-censored at the earlier of the date the participant was last known alive and clinical data cutoff date for the analysis. The last known alive date is defined as the later of the last study visit and the date the participant was last known alive from the Survival Follow-up and Participant Status eCRFs. The partial death dates will be handled using the rules described in Section 4.1.4.

The OS will be analyzed by the KM method in Cohort A. The number of participants who died and the number of participants censored will be summarized. The median survival will be estimated using the KM method. The 95% CIs for median survival time will be calculated using the generalization of Brookmeyer and Crowley's method (1982) with log-log transformation (Klein and Moeschberger 1997).

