7.5. Analysis of Exploratory Efficacy Variables

The PFS, DOR (ie, per RECIST v1.1 and as assessed by ICR), and OS in Cohort B will be analyzed for the FAS in the same fashion as Cohort A.

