10.1. Changes to Protocol-Defined Analyses

A decision was made to terminate study enrollment. At the time of study termination there were fewer than 10 participants enrolled; as a result, an interim futility analysis and a sensitivity analysis will not be conducted. The RECIST-evaluable population and the Per-Protocol population will not be generated for analysis.

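### The 95% label on the Kaplan-Meier median interval does not hold for groups of 2 to 4, the likely size of the duration-of-response analysis

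*SAP*

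**What the plan says.** The only SAP version is dated 20 OCT 2023. Section 10.1 states: "At the time of study termination there were fewer than 10 participants enrolled". For that reason it drops the futility analysis, the sensitivity analysis and two analysis populations. The time-to-event summaries were not adapted in the same way:

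- PFS, section 7.3.2: "The KM estimates of median PFS will be presented with its 95% CI".
- DOR, section 7.3.3: "The KM estimate of median DOR will be presented with its 95% CI". The method is the "generalization of Brookmeyer and Crowley's method (1982) with log-log transformation", applied to objective responders only.
- OS, section 7.3.4: "The 95% CIs for median survival time will be calculated using the generalization of" the same method.
- Cohort B, section 7.5: PFS, DOR "and OS in Cohort B will be analyzed for the FAS in the same fashion as Cohort A".

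Section 3.2 sets the level: "Unless otherwise specified, all CIs provided will be at the 95% confidence level". Tables 2.2.2 to 2.2.4 for Cohort A remain planned. Sections 7.3.2 to 7.3.4 and 7.5 set no minimum number of participants, responders or events. They do not call the interval approximate, and they give no rule for a limit that cannot be estimated. Section 8.1 allows tables to be replaced by listings, but only for safety. The ORR interval is Clopper-Pearson, which is exact and not affected.

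**The concern.** The Brookmeyer-Crowley interval inverts a normal-theory test on the Kaplan-Meier curve using Greenwood's variance. That variance is zero before the first event, so the lower limit cannot fall below the first event time however few people are in the group. With two or three responders, the chance that all of them outlast the true median is large compared with 5%. Followed as written, the SAP would print such a lower limit as part of a 95% interval. A median DOR taken from the report without its group size would then carry more confidence than the data give it, and the miss would lie on the side that overstates duration.

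**Working it through.** **Inputs.** Fewer than 10 participants, so at most 9 (SAP 10.1). Confidence level 95%, taken as two-sided (SAP 3.2). Log-log Brookmeyer-Crowley (SAP 7.3.2 to 7.3.4). Assumed ORR 40% (SAP 3.3). The cohort split, the number of responders and the amount of censoring are not given, so ranges are shown.

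**Method.** The interval contains the times t at which |log(−log S(t)) − log(−log 0.5)| / se ≤ 1.96, with se = √(Greenwood sum) / |log S(t)|. Without censoring, the number of events before the true median is X ~ Binomial(n, 0.5), so coverage is exact. A limit that cannot be estimated counts as open.

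**The plan's own figure at the planned sizes.** At n=100 the interval runs from the 40th to the 60th event, and coverage is 1 − 0.0176 − 0.0284 = 95.4%. At n=25 it runs from the 8th to the 18th, and coverage is 1 − 2 × 0.0216 = 95.7%. The label is sound there.

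**Lower limit in small groups.** At the first event S = (n−1)/n and the Greenwood sum is 1/(n(n−1)). For n=3: S = 0.667, se = 0.408/0.405 = 1.007, and the statistic is |−0.903 + 0.367| / 1.007 = 0.53. This is below 1.96, so the first event time is the lower limit. The same holds for every n from 2 to 10 (1.88 at n=10; 1.98 at n=11). The lower limit exceeds the true median when all n times do, with probability 0.5^n.

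**Upper limit.** At the second-to-last event S = 1/n and the Greenwood sum is (n−1)/n. The statistic is 0.62 at n=3, 1.11 at n=4, 1.86 at n=6 and 2.17 at n=7. At the last event S = 0 and the transform is undefined. So there is no upper limit for n=2 to 6. For n=7, 8 and 9 it is the 6th, 7th and 8th event.

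**Coverage without censoring.**

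| n | Miss low | Miss high | Coverage |
|---|---|---|---|
| 2 | 1/4 | none | 75.0% |
| 3 | 1/8 | none | 87.5% |
| 4 | 1/16 | none | 93.75% |
| 5 | 1/32 | none | 96.9% |
| 6 | 1/64 | none | 98.4% |
| 7 | 1/128 | 8/128 | 93.0% |
| 8 | 1/256 | 9/256 | 96.1% |
| 9 | 1/512 | 10/512 | 97.9% |

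With n=1 there is no interval.

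**With censoring** (simulated; exponential event and censoring times are an assumption; 40,000 runs per n; among runs where a lower limit exists):

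- 25% censored: 84.6%, 87.9% and 92.1% at n=2, 3 and 4; 95.5% to 97.4% at n=5 to 9.
- 50% censored: 93.9% to 94.7% at n=2 to 4; 95.7% to 97.1% at n=5 to 9.

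**How likely 2 to 4 responders are at 40% ORR**, given at least one: [P(X≤4) − P(X≤1)] / [1 − 0.6^N].

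- N=5: (0.9898 − 0.3370) / 0.9222 = 71%.
- N=7: (0.9037 − 0.1586) / 0.9720 = 77%.
- N=9: (0.7334 − 0.0705) / 0.9899 = 67%.

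At 20% ORR the same formula, with 0.8^N in place of 0.6^N, gives (0.9997 − 0.7373)/0.6723 = 39%, (0.9953 − 0.5767)/0.7903 = 53% and (0.9804 − 0.4362)/0.8658 = 63%. Most of the remainder is a single responder, for whom no interval exists.

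**The case against.** The strongest reply is that little turns on these limits. SAP 7.1 states no efficacy hypothesis, enrollment was terminated, and the medians are secondary or exploratory descriptions. The numbers of responders, events and censored participants stand beside the DOR median, and Listing 2.6.2 gives the individual results. A reader who sees a first event time paired with an upper limit that is not estimable will know that the data say little. All of this stands, and it sets the severity. It does not make the label correct.

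Four stronger readings are tempting and not supported:

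- *All the PFS, OS and Cohort B intervals fail.* PFS and OS use the whole cohort, and at 5 to 9 members coverage is about 95% or more apart from n=7 without censoring. With at most 9 people in two cohorts, the smaller cohort has at most 4. It may also have none or one, and the SAP does not say which cohort it is. If it is Cohort B, Appendix A plans no time-to-event table for it.
- *Coverage falls to 50%, 75% and 87.5% at n=2, 3 and 4.* Those figures require closing the interval at the last event, which the SAP does not say.
- *The DOR group is almost always too small.* With 9 in Cohort A at 40% ORR, P(4 or fewer responders, given at least one) is 73%, and with 5 it is 99%. Both figures include a single responder, where there is no interval to mislabel.
- *The error favours the drug.* The low-side miss does overstate duration, but no rule or claim in the SAP depends on that limit.

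**Conclusion.** The point holds for small groups only. With 2, 3 or 4 uncensored members the stated 95% is really 75%, 87.5% or 93.75%. Under the censoring assumed here it stays below 95%, at 84.6% to 94.7%. For DOR this is the likely situation at the planned 40% response rate; at 20% a single responder becomes more common. For PFS and OS the label is not guaranteed, rather than shown to fail, unless a cohort has 4 or fewer participants. The result rests on an open upper limit where none can be estimated and, for the censored figures, on exponential times. Severity is minor: the summaries are descriptive and no decision is attached to them.

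**What to change.** Add a rule to SAP 7.3.2, 7.3.3, 7.3.4 and 7.5:

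- If the analysis group (responders for DOR) has fewer than 5 members, report no 95% CI for the median. Give the median and the individual times from Listing 2.6.2, with censoring flags. This also settles the case of one responder.
- If the group has 5 to 9 members, label the interval approximate.

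Alternatively, use an interval valid in small samples throughout, such as the beta product confidence procedure for the Kaplan-Meier median.

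A cut at 6 instead of 5 would follow only from requiring 2.5% in each tail (at n=5 the low-side miss is 1/32 = 3.1%). SAP 3.2 promises only an overall 95% level, which n=5 meets without censoring.

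The cost is a sentence or two of SAP text and minor programming. Some intervals will be wider or not reported.

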7.3.4. Overall Survival

Overall survival is defined as the time from the date of first dose of pemigatinib to the date of death due to any cause. Date of death will be determined using Death Report, Survival Follow-up, and Participant Status eCRFs. Participants who are lost to follow-up or still alive at the time of the analysis will be right-censored at the earlier of the date the participant was last known alive and clinical data cutoff date for the analysis. The last known alive date is defined as the later of the last study visit and the date the participant was last known alive from the Survival Follow-up and Participant Status eCRFs. The partial death dates will be handled using the rules described in Section 4.1.4.

The OS will be analyzed by the KM method in Cohort A. The number of participants who died and the number of participants censored will be summarized. The median survival will be estimated using the KM method. The 95% CIs for median survival time will be calculated using the generalization of Brookmeyer and Crowley's method (1982) with log-log transformation (Klein and Moeschberger 1997).

7.4. Analysis of Other Efficacy Parameters

[figure not shown]
7.4.1. Largest Percentage Reduction in Sum of Diameters of Target Lesions

[figure not shown]
For each participant in the FAS with measurable target lesions at baseline, target lesion sizes will be measured by sum of diameters. The best percentage change from baseline, defined as the largest decrease in target lesion size for each participant during the study, will be listed.

Per RECIST criteria, target lesions considered "too small to measure" will be assigned a default value of 5 mm for purposes of this analysis. Likewise, target lesions identified as "not present" at postbaseline assessments will be assigned 0 mm for this analysis. In the event a target lesion is unaccounted for in a particular postbaseline timepoint (ie, assessment missing or not evaluable), then the overall sum of diameters for target lesions will not be evaluable for that postbaseline timepoint.

7.5. Analysis of Exploratory Efficacy Variables

The PFS, DOR (ie, per RECIST v1.1 and as assessed by ICR), and OS in Cohort B will be analyzed for the FAS in the same fashion as Cohort A.

7.5.2. Eastern Cooperative Oncology Group Performance Status

The ECOG performance status at scheduled assessment times will be listed by treatment cohorts.

8. SAFETY AND TOLERABILITY

[Appendix A](#) provides a list of data displays.

8.1. General Considerations

The analyses for this section will be provided for the safety population. Summary tables may be replaced with listings when appropriate. For instance, an AE frequency table may be replaced with a listing if it only contains a few unique PTs reported on relatively few participants.

8.2. Adverse Events

8.2.1. Adverse Event Definitions

A TEAE is any AE either reported for the first time or worsening of a pre-existing event after the first dose of study treatment until 30 days of the last dose of study treatment. Analysis of AEs (as discussed below) will be limited to TEAEs, but data listings will include all AEs regardless of their timing and in relation to study treatment administration. For purposes of analysis, all AEs will be considered TEAEs unless the AE can unequivocally be defined as not treatment-emergent.

Adverse events will be listed by Medical Dictionary for Regulatory Activities PT and system organ class. Severity of AEs will be graded using the NCI CTCAE v5.0. The CTCAE reporting guidelines and grading details are available on the Cancer Therapy Evaluation Program website.

A grading (severity) scale is provided for each AE term. If the toxicity is not included in the CTCAE v5.0 criteria, it will be rated on a scale of 1 to 5 as follows: 1 = mild, 2 = moderate, 3 = severe, 4 = life-threatening, and 5 = fatal. All toxicities will be graded based on the worst level reached, not the level they may have reached if they had not been treated. When the intensity of an AE changes over time for a reporting period (eg, between visits), each change in intensity will be reported as an AE until the event resolves.

The subset of AEs considered by the investigator to be related to study drug will be considered to be treatment-related AEs. If the investigator does not specify the relationship of the AE to study drug, the AE will be considered to be treatment-related. The incidence of AEs and treatment-related AEs will be listed. In addition, serious TEAEs and serious AEs will be listed.

Any missing data pertaining to date of onset, causality, or severity of an AE must be queried for resolution. Unresolved missing causality or severity of an AE will be handled according to the following rules:

- An unresolved missing causality will be considered treatment-related.
- An unresolved missing severity will be identified as an unknown severity.

8.2.2. Adverse Event Listings

The following listings will be produced:

- Listing of AEs
- Listing of serious AEs
- Listing of Grade 3 or higher AEs
- Listing of AEs with a fatal outcome
- Listing of pemigatinib treatment-related AEs
- Listing of AEs leading to interruption, reduction, or discontinuation of pemigatinib

